APPENDIX E

LIST)F FIGURES
MedImmune	; Final Version 7.0
MEDI-563	Protocol #MI-CP166
	Page 7 of 91

Figure 1	Study Schema	1	9
----------	--------------	---	---

MEDI-563 MedImmune	CONFIDENTIAL	Page 8 of 91 Protocol #MI-CP166 Final Version 7.0
	LIST OF TABLES	
Table 1	Summary of Study Drug Administration in Cohort 1	
Table 2	Summary of Study Drug Administration in Cohort 2	
Table 3	Intravenous Administration in Cohort 1	
Table 4	Study Schedule for Cohort 1	
Table 5	Study Schedule for Cohort 2	
Table 6	Expected Number of Subjects with AEs and Probabilities of Obse or 2 Subjects with AEs Given the True Event Rates	erving at Least 1 64
Table 7	Estimated AE Rates and 95% Exact Binomial Confidence Interva Number of Subjects with AEs Observed	ls Given the 64
Table 8	Probability of Observing the Point Estimate of the Percent Chang $\geq 80\%$ or 60% in Eosinophil Counts in Airway Mucosal Biopsies	e from Baseline 64

STUDY ABSTRACT

TITLE:

A Phase 1, Double-Blind, Placebo-Controlled Study To Evaluate the Safety, Tolerability and Effects of MEDI-563, A Humanized Anti-Interleukin-5 Receptor Alpha Monoclonal Antibody, On Airway Eosinophils in Adults with Asthma

OBJECTIVES:

The primary objectives of this study are to:

- 1. Evaluate the safety and tolerability of MEDI-563 in adults with asthma; and
- 2. Evaluate the effects of MEDI-563 on eosinophil counts in airway mucosal biopsies 28 days after completion of dosing in adults with asthma.

The secondary objectives of this study are to:

- 1. Evaluate the pharmacokinetics (PK) of MEDI-563 in adults with asthma; and
- 2. Evaluate the immunogenicity (IM) of MEDI-563 in adults with asthma.

The exploratory objectives of this study are to:

- 1. Evaluate the effects of MEDI-563 on disease activity;
- 2. Evaluate the effects of MEDI-563 on inflammatory cells and proteins in mucosal biopsies, including eosinophils in mucosal biopsies;
- 3. Evaluate the effects of MEDI-563 on inflammatory cells and proteins in induced sputum;
- 4. Evaluate the effects of MEDI-563 on eosinophils and eosinophil precursors in bone marrow in adults with asthma;
- 5. Evaluate the effects of MEDI-563 on peripheral blood levels of eosinophil and basophil derived proteins and cytokines in adults with asthma;
- 6. Evaluate the effects of MEDI-563 on peripheral blood eosinophil and basophil counts;
- 7. Evaluate downstream effects of MEDI-563 on mRNA levels in whole blood, using microarray analyses; and
- 8. Explore single-nucleotide-polymorphisms and microsatellite or short tandem repeat analyses for genes associated with asthma in whole blood DNA, if such analyses are warranted based on other exploratory analyses in adults with asthma.

DESIGN:

This is a Phase 1, randomized, double-blind, placebo-controlled study to evaluate the safety, tolerability, and effects of single IV and multiple SC administration of MEDI-563 on airway eosinophils in adults with asthma who have $\geq 2.5\%$ eosinophils in sputum. A total of up to 24 subjects are expected to be enrolled at approximately 10 investigative sites in the USA and Canada.

The first 12 subjects will be randomized in a 2:1 ratio to receive a single IV dose of MEDI-563 (1.0 mg/kg) or placebo (Cohort 1), with 8 subjects receiving MEDI-563 and 4 subjects receiving placebo. This cohort may be expanded by up to 3 additional subjects (for a maximum of 15 subjects) if eligible subjects are already in screening at the time 12 subjects have been randomized into the dose cohort. On Study Day 28, these subjects will undergo an airway biopsy. Decisions regarding whether to proceed with single-dose cohorts or multiple-dose cohorts were to be based on biopsy results as follows:

- If the airway biopsy results from subjects treated with MEDI-563 indicate a mean reduction in eosinophil count of ≥ 80% from baseline (Study Day 0), subsequent cohorts will receive reduced single IV doses of MEDI-563 or placebo.
- If the airway biopsy results from subjects treated with MEDI-563 indicate a mean reduction in eosinophil count of < 80% from baseline (Study Day 0), subsequent cohorts will receive multiple IV doses of MEDI-563 or placebo.

The decision tree above was removed to include the evaluation of multiple-dose SC administration (100 mg and 200 mg) instead of single or multiple-dose IV administration of MEDI-563 due to the development of the SC formulation of MEDI-563 and the intent to proceed with multiple-dose SC administration in the future.

A total of 13 subjects received a single IV dose of MEDI-563 (1.0 mg/kg) or placebo (Cohort 1) in this study under previous versions of the study protocol. Cohort 1 completed the study, and the data remain blinded per protocol.

A second group of 12 subjects (Cohort 2) will be randomized in a 1:1:1 ratio to receive 1 of 2 doses of MEDI-563 (100 mg or 200 mg) or placebo as an SC injection once every 4 weeks for 8 weeks (Study Day 0, Study Day 28, and Study Day 56). This cohort may be expanded by up to 3 additional subjects (for a maximum of 15 subjects) if eligible subjects are already in screening at the time 12 subjects have been randomized into the dose cohort.

Subjects will be screened for up to 14 days. Study drug administration will occur on Study Day 0 for Cohort 1 and on Study Days 0, 28, and 56 for Cohort 2. All subjects will be followed for at least 12 weeks after study drug administration (through Study Day 84 for Cohort 1 and through Study Day 140 for Cohort 2). Bronchoscopies with biopsies consisting of 4-6 subsegmental and segmental biopsies in each procedure will be performed at 2 time points during the study (screening and Study Day 28 for Cohort 1 or screening and Study Day 84 for Cohort 2). For Cohort 1 only, an additional optional bronchoscopy and biopsies may be performed on Study Day 84.

SUBJECT POPULATION:

The subjects in this study will be adults with asthma who have $\geq 2.5\%$ eosinophils in sputum.

TREATMENT:

Subjects in Cohort 1 will receive either MEDI-563 (1.0 mg/kg) or placebo as an IV infusion, with 8 subjects receiving MEDI-563 and 4 subjects receiving placebo. This cohort may be expanded by up to 3 additional subjects (for a maximum of 15 subjects) if eligible subjects are already in screening at the time 12 subjects have been randomized into the dose cohort. All infusions must be administered with a 0.22 μ m protein-sparing/low in-line filter, which will be supplied by the sponsor. All doses must be administered over at least 30 minutes.

Cohort	Ν	Treatment
1	12	1.0 mg/kg IV: MEDI-563 (N=8) / Placebo (N=4) on Study Day 0

Subjects in Cohort 2 will receive 1 of 2 doses of MEDI-563 (100 mg or 200 mg) or placebo as an SC injection once every 4 weeks on Study Days 0, 28, and 56. Four subjects will receive each MEDI-563 dose and 4 subjects will receive placebo. This cohort may be expanded by up to 3 additional subjects (for a maximum of 15 subjects) if eligible subjects are already in screening at the time 12 subjects have been randomized into the dose cohort. The study drug will be administered by injection into the SC tissue of the triceps muscle of the arm.

Cohort	N	Treatment
	4	100 mg SC MEDI-563 on Study Days 0, 28, and 56
2	4	200 mg SC MEDI-563 on Study Days 0, 28, and 56
	4	Placebo SC on Study Days 0, 28, and 56

SUBJECT EVALUATION AND FOLLOW-UP:

Subjects in Cohort 1 will be screened for up to 14 days, and then study drug administration will occur on Study Day 0, and subjects will be followed for at least 12 weeks after study drug administration. Bronchoscopies with biopsies consisting of 4-6 subsegmental and segmental biopsies in each procedure will be performed at least at 2 time points during the study (and Study Day 28) with an additional optional bronchoscopy and biopsies performed on Study Day 84. Safety and efficacy evaluations for subjects in Cohort 1, including assessment of adverse events (AEs) and serious adverse events (SAEs), will be performed from screening through at least End of Study/Study Termination (Study Day 84).

Subjects in Cohort 2 will be screened for up to 14 days, and then study drug administration will occur on Study Days 0, 28, and 56. Subjects will be followed for at least 12 weeks after study drug administration. Bronchoscopies with biopsies consisting of 4-6 subsegmental and segmental biopsies in each procedure will be performed at 2 time points during the study (screening and Study Day 84).

If, at the End of Study/Study Termination visit (Study Day 84 for Cohort 1 or Study Day 140 for Cohort 2), a subject's eosinophil count in peripheral blood is not at least 100 eosinophils/mm³ OR the peripheral blood eosinophil count has not returned to at least 70% of the baseline value, the subject will return to the study site every other month until the subject's eosinophil count meets one of the criteria above.

ASSESSMENT OF ENDPOINTS:

The primary endpoints of this study are to evaluate the safety and tolerability of MEDI-563 and to evaluate the effect of MEDI-563 on airway mucosal eosinophils 28 days after completion of dosing in adults with asthma. Safety and tolerability will be assessed by summarizing AEs. The occurrence of AEs will be reported from the time the subject signs the informed consent through End of Study/Study Termination (Study Day 84 for Cohort 1 or Study Day 140 for Cohort 2). The occurrence of SAEs will be reported from the time the subject signs the informed consent through End of Study/Study Termination (Study Day 84 for Cohort 1 or Study Day 140 for Cohort 2), or until the long-term follow-up period is complete, if applicable. Other variables used for the safety assessments include serum chemistry, complete blood count (CBC) with differential and platelets, and urinalysis. These variables as well as their changes from baseline will be summarized descriptively. Percent change from baseline in eosinophil counts in the airway mucosa (Study Day 28 for Cohort 1 or Study Day 84 for Cohort 2) will be summarized by cohort and treatment group.

The secondary endpoints of this study are to evaluate the PK and IM of MEDI-563. Noncompartmetal pharmacokinetic parameters to be reported include but are not limited to, the maximum observed plasma concentration of MEDI-563 (C_{max}), area under the concentration-time curve (AUC), the terminal elimination half-life ($t_{1/2}$) and systemic clearance (CL) for Cohort 1, if the data allow. For Cohort 2, C_{max} and pre-dose trough (C_{min}) plasma concentrations will be summarized following each dose. Descriptive statistics of these noncompartmental parameters by dose cohort will also be provided. Immunogenicity will be evaluated by analyzing plasma samples for the detection of the presence of anti-MEDI-563 antibodies following MEDI-563 dosing. Immunogenicity results will be listed for each subject, and the percentage of subjects who developed detectable anti-MEDI-563 antibodies will be calculated and reported.

Exploratory endpoints include examining evidence of the clinical activity of MEDI-563. Spirometry endpoints will be evaluated using indicators including forced expiratory volume in 1 second (FEV₁) and forced vital capacity (FVC). Other changes in disease activity, such as peak morning flow, Asthma Control Questionnaire (ACQ), use of rescue β2 agonist medication, and Asthma Quality of Life Questionnaire (Standardized Version) [AQLQ(S)] will be evaluated in the MEDI-563 and placebo groups. Sputum inflammatory cells, number of bone marrow eosinophils and eosinophil precursors, serum levels of eosinophil- and basophil-derived proteins and inflammatory cytokines, cells in airway mucosal biopsies, downstream effects of MEDI-563 on mRNA levels in whole blood, and exploration of single-nucleotide-polymorphisms and microsatellite or short tandem repeat analyses in whole blood DNA. All these endpoints and corresponding change from baseline will be summarized by cohort and treatment group.

All endpoints will be summarized by cohort and treatment group.

1 INTRODUCTION

1.1 Background

1.1.1 Overview of Asthma

Asthma is a syndrome characterized by airway inflammation, reversible variable airway obstruction, and airway hyperresponsiveness (AHR). Subjects with asthma may have chronic inflammation of the airways even when in clinical remission (van den Toorn et al, 2001). Progressive pathologic airway remodeling and scarring may result in partially reversible or irreversible airway obstruction (Pascual and Peters, 2005).

Asthma is a critical clinical and public health problem in the United States of America (USA) and the rest of the world. As of 2003, approximately 10.4% of people in the USA, or 30 million people, had a history of asthma sometime in their lifetime (Centers for Disease Control, 2003). Of this cohort, the prevalence of current asthma was 20 million. Estimates are that nearly half of all current asthmatics have moderate or severe asthma, with 31% having moderate persistent asthma and 16% having severe persistent asthma (Stoloff, 2000).

The National Heart, Lung, and Blood Institute has provided guidelines for the treatment of asthma. The major goals of asthma therapy are to prevent chronic asthma symptoms and asthma exacerbations during the day and night, as indicated by no sleep disruption, no missed work or school, and no or minimal need for emergency room (ER) visits or hospitalizations. Current therapies for asthma consist of long-term control medications and rescue medications for acute exacerbations. The most effective long-term control medications for asthma are those that reduce inflammation. Inhaled corticosteroids (ICS) are the most potent anti-inflammatory medication currently available for persistent asthma; long-term use of ICS may lead to adverse effects. Other long-term control medications for acute estabilizers, leukotriene modifiers, and combination therapies. Rescue medications are used to provide prompt treatment of acute airflow obstruction and its accompanying symptoms. These medications include primarily short-acting bronchodilators including short-acting $\beta 2$ agonists have been associated with increased mortality (Nelson et al, 2006; Anderson et al, 2005). There is a need for additional effective treatment for asthma to achieve optimal outcomes for subjects.

1.1.2 Role of Eosinophils in Asthma

Eosinophils are thought to play a critical role in the pathogenesis and severity of asthma. Reduction of eosinophils in sputum has been shown to be associated with better asthma control (Green et al, 2002) and increases in sputum eosinophilia are associated with exacerbations of both asthma and chronic obstructive pulmonary disease (COPD) (Scott and Wardlaw, 2006).

Interleukin-5 (IL-5) is a cytokine secreted predominantly by T-lymphocytes, mast cells, and eosinophils and is involved in regulating the differentiation, proliferation, and activation of eosinophils via the IL-5 receptor (IL-5R). The IL-5R is a heterodimer consisting of an α -chain and a β -chain. Monomeric IL-5R α are low affinity receptors, while dimerization with the β -chain

produces a high affinity receptor (Tavernier et al, 1991). In the absence of IL-5 interaction with the α -chain, binding to the β -chain alone by the ligand does not occur.

Expression of the IL-5R α chain is restricted largely to eosinophils, basophils, and some mast cells in humans (Toba et al, 1999; Dahl et al, 2004). The α -chain exclusively binds IL-5 and the intracellular portion of IL-5R α is associated with Janus kinase 2, a protein tyrosine-kinase essential in IL-5 signal transduction (Ogata et al, 1998; Takaki et al, 1994).

Thus, IL-5R α may be a good target for a therapeutic antibody in the management of asthma. Eosinophils, and perhaps basophils and some mast cells, can be preferentially targeted for antibody-dependent cell cytotoxicity (ADCC) through IL-5R α , depleting cells thought to be key in disease pathogenesis and severity. In addition, blocking of IL-5R α could provide benefit by neutralizing effects of IL-5. Previous clinical studies with an anti-IL5 monoclonal antibody (MAb) failed to show reductions in AHR or increases in forced expiratory volume in 1 second (FEV₁) and peak expiratory flow rate (PEFR). The anti-IL5 MAb was associated with incomplete depletion (mean 55%) of eosinophils in the airways, leading to the hypothesis that incomplete depletion of eosinophils in the airways explained lack of clinical effect (Flood-Page et al, 2003). The purpose of this study is to test whether a MAb that targets IL-5R α , rather than IL-5, and is engineered to augment ADCC (MEDI-563) would provide near complete (more than 80%) reduction in airway eosinophils. This characteristic of MEDI-563 would provide the opportunity to test in future studies whether complete depletion of eosinophils in the airways is associated with therapeutic benefit in asthma.

1.2 Description of MEDI-563

MEDI-563 (formerly known as BIW-8405) is a recombinant, a-fucosylated, humanized MAb to the IL-5R α . The MAb was humanized by replacing mouse for human constant regions of the IgG_{1 κ} isotype and is composed of 2 heavy chains (IgG1) and 2 light chains (kappa), with a molecular weight of approximately 150 kilodaltons. Fucose was removed from glycosylation to increase ADCC activity of MEDI-563.

1.3 Nonclinical Experience with MEDI-563

In vitro studies have shown that MEDI-563 binds to eosinophils through the IL-5R α , and blocks the binding of the ligand, IL-5 to the receptor and activates effector cells for expression of ADCC activity causing the apoptosis of eosinophils. In addition, studies in a number of in vivo models (cynomolgus monkey) of peripheral eosinophilia and allergic asthma demonstrated that MEDI-563 would work in vivo as an anti-eosinophil therapeutic reagent. The close similarity between human and cynomolgus monkey tissue cross-reactivity profiles confirmed that the cynomolgus monkey was an appropriate animal species for study.

Toxicology studies were conducted in cynomolgus monkeys following intravenous (IV) and subcutaneous (SC) administration of MEDI-563. MEDI-563 was administered IV once every 3 weeks for 9 weeks (on Days 1, 22, 43, and 64) at dose levels of 0 (control), 0.1, 1.0, 10.0 and 30 mg/kg with an 18-day recovery period to evaluate reversibility of any MEDI-563 effects. A marked depletion of peripheral blood eosinophils was evident shortly after dose initiation at all

dose levels and persisted throughout the study. Decreased leukocyte levels which resulted from differential decreases in neutrophils were transiently seen in one high-dose (30.0 mg/kg) male and one high-dose female during the dosing period. The observed eosinophil depletion from peripheral blood was an anticipated pharmacological effect of the test article and no other signs of test article treatment were observed in any of the other in-life or post-mortem examinations and assessments of the study. In addition, depletion of eosinophil progenitors was evident in the bone marrow without affecting the neutrophil lineage. Under the conditions of the study, the no-observed-adverse-effect level (NOAEL) for MEDI-563 was \leq 30.0 mg/kg; the neutrophil change noted in 2 of 10 animals treated in the 30.0 mg/kg group was mild and temporary.

When MEDI-563 (1, 10, or 30 mg/kg) was administered to cynomolgus monkeys as a SC injection every other week for 15 weeks (8 total doses), no adverse test article-related changes were identified, resulting in a NOAEL of at least 30 mg/kg, the highest dose tested.

Additional nonclinical information can be obtained from the Investigator Brochure.

1.4 Clinical Experience with MEDI-563

MEDI-563 is being evaluated in 4 clinical studies, including the current study. One study has completed enrollment and data analysis is ongoing (MI-CP158) and the remaining 3 studies are ongoing (MI-CP166, MI-CP186, and MI-CP197). All clinical studies are being conducted in adult subjects with asthma.

The first clinical study of MEDI-563 in humans was MI-CP158, a Phase 1, open-label, doseescalation study evaluating the safety and tolerability of single IV doses of MEDI-563 (0.003 to 3 mg/kg) in adult subjects with mild asthma. This study has completed enrollment and data analysis is ongoing. A total of 44 subjects have received a single IV dose of MEDI-563 in this study. MEDI-563 was well tolerated in this study. The majority (>85%) of adverse events (AEs) were mild in severity, and there were no deaths, serious adverse events (SAEs), severe AEs, nor any AEs that resulted in MEDI-563 discontinuation. The most common AE was decreased white blood cell count. This finding is consistent with the mechanism of MEDI-563 (ie, depletion of eosinophils in peripheral blood). Another common AE was mild elevations in blood creatine phosphokinase (CPK). A single IV dose of MEDI-563, as low as 0.03 mg/kg, depleted eosinophils in peripheral blood to below the level of detection for at least 8 weeks. In the highdose groups (1.0 and 3.0 mg/kg), the eosinopenia in peripheral blood lasted up to 12 to 16 weeks, respectively. Conversely, in the low-dose groups (0.003 and 0.0003 mg/kg) eosinopenia in peripheral blood lasted an average of 2 weeks and 1 to 2 days, respectively, demonstrating that the effects of MEDI-563 are dose-dependent.

MI-CP186 is a Phase 2, randomized, double-blind, placebo-controlled study evaluating the effect of two IV dose regimens of MEDI-563 (0.3 and 1.0 mg/kg) on the asthma exacerbation rate (relapse and de novo) in adult subjects who required an urgent healthcare visit for treatment of an acute asthma exacerbation.

MI-CP197 is a Phase 2a, randomized, double-blind, placebo-controlled, dose-escalation study evaluating the safety, tolerability, PK, and immunogenicity (IM) of multiple SC doses of MEDI-

563 (25, 100, and 200 mg) in adult subjects with asthma. All subjects have been treated with no serious safety issues reported.

In the current study (MI-CP166), a total of 13 subjects (Cohort 1) received a single IV dose of MEDI-563 (1.0 mg/kg) or placebo and completed the study according to the protocol. Data remain blinded as per protocol. No SAEs have occurred in any of the subjects in Cohort 1.

Additional clinical information can be obtained from the Investigator Brochure.

1.5 Rationale for Study

This is a Phase 1, randomized, double-blind, placebo-controlled study to evaluate the safety, tolerability, and effect of single IV or multiple SC administration of MEDI-563 on airway eosinophils in adults with asthma who have $\geq 2.5\%$ eosinophils in sputum. This inclusion criterion was selected because in the presence of asthma it may identify subjects with higher numbers of eosinophils in airway mucosal biopsies (Lemiere et al, 2006). Previous experience with another anti-IL-5 monoclonal antibody has shown that a dose that provokes less than 60% mean reduction of eosinophils in airway mucosa is unlikely to be clinically effective in asthma (Green et al, 2002).

Initially, 12 subjects will be randomized in a 2:1 ratio to receive a single IV dose of MEDI-563 (1.0 mg/kg) or placebo (Cohort 1). Airway biopsies will be done on Study Day 28. Biopsy results were to be evaluated to determine if the study will continue as a single-dose reduction study or a multiple-dose escalation study. The criterion for this decision was as follows:

- If the Study Day 28 airway biopsy results from Cohort 1 MEDI-563 subjects show the mean number of eosinophils in airway mucosa is reduced from baseline by 80% or more, subsequent cohorts of 12 subjects each (randomized in a 2:1 ratio) will receive a single lower dose of MEDI-563 (0.3, 0.03, 0.003 mg/kg) or placebo until either the dose that provokes less than a 60% mean reduction of eosinophils in airway mucosa is reached or the 0.003 mg/kg dose cohort is enrolled.
- If the Study Day 28 airway biopsy results from Cohort 1 MEDI-563 subjects show the mean number of eosinophils in airway mucosa is reduced from baseline by less than 80%, subsequent cohorts of 12 subjects each (randomized in a 2:1 ratio to receive MEDI-563 or placebo) will receive 4 treatments (every 3 weeks) of MEDI-563 (0.3, 1.0, or 3.0 mg/kg) or placebo until either the dose that provokes a 80% or more mean reduction of eosinophils in airway mucosa or the 3.0 mg/kg dose cohort is enrolled.

The decision tree above was removed to include the evaluation of multiple-dose SC administration (100 mg and 200 mg) instead of single or multiple-dose IV administration of MEDI-563 due to the development of the SC formulation of MEDI-563 and the intent to proceed with multiple-dose SC administration in the future.

A total of 13 subjects received a single IV dose of MEDI-563 (1.0 mg/kg) or placebo (Cohort 1) in this study under previous versions of the study protocol. Cohort 1 completed the study, and the data remain blinded per protocol.

A second group of 12 subjects (Cohort 2) will be randomized in a 1:1:1 ratio to receive 1 of 2 doses of MEDI-563 (100 mg or 200 mg) or placebo as an SC injection once every 4 weeks for 8 weeks (Study Day 0, Study Day 28, and Study Day 56). This cohort may be expanded by up to 3 additional subjects (for a maximum of 15 subjects) if eligible subjects are already in screening at the time 12 subjects have been randomized into the dose cohort.

All subjects will be followed for at least 12 weeks after the last dose of study drug (anticipated to be greater than 5 half-lives of the study drug). If, at the End of Study/Study Termination visit (Study Day 84 for Cohort 1 or Study Day 140 for Cohort 2), a subject's eosinophil count in peripheral blood is not at least 100 eosinophils/mm³ OR the peripheral blood eosinophil count has not returned to at least 70% of the baseline value, the subject will return for follow-up every other month until the eosinophil count meets one of the criteria above.

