3.6 Completion of Study and Loss to Follow-up

For Cohort 1, subjects will be considered to have completed the study if they were followed up through Study Day 84. For Cohort 2, subjects will be considered to have completed the study if they were followed through Study Day 140. It should be specified on the CRF whether or not the subject completed the study through End of Study/Study Termination (Study Day 84 for Cohort 1 or Study Day 140 for Cohort 2).

Subjects will be considered lost-to-follow-up only if no contact has been established by the time the study is completed such that there is insufficient information to determine the subject's status at Study Day 84 for Cohort 1 subjects and Study Day 140 for Cohort 2 subjects. Investigators or their qualified designees should document attempts to re-establish contact with missing subjects throughout the study period. If contact with a missing subject is re-established, follow-up should resume according to the protocol.

Any subject whose eosinophil count in peripheral blood is not at least 100 eosinophils/mm³ OR has not returned to at least 70% of the baseline value at the End of Study/Study Termination (Study Day 84 for Cohort 1; Study Day 140 for Cohort 2) will be asked to return to the site every other month until the eosinophil count in peripheral blood meets one of the criteria above.

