4.2.2 Study Reporting Period for Serious Adverse Events

For Cohort 1, the reporting period for SAEs is from the time the subject signs the informed consent through Study Day 84 or until eosinophil levels in peripheral blood are at least 100 eosinophils/mm³ OR the peripheral blood eosinophil count has returned to at least 70% of the baseline value, if applicable.

For Cohort 2, the reporting period for SAEs is from the time the subject signs the informed consent through Study Day 140 or until eosinophil levels in peripheral blood are at least 100 eosinophils/mm³ OR the peripheral blood eosinophil count has returned to at least 70% of the baseline value, if applicable.

After the initial SAE report the investigator is required to follow each subject proactively and provide further information on the subject's condition to MedImmune Product Safety.

All SAEs should be followed up to resolution by the investigator, even if this extends beyond the study reporting period. Resolution of a SAE is defined as the return to baseline status or stabilization of the condition with the expectation that it will remain chronic.

At any time after completion of the study, if an investigator or qualified designee becomes aware of a SAE that is suspected by the investigator or qualified designee to be related to study product, the event should be reported to MedImmune Product Safety.

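### Long-term eosinophil follow-up is entered by failing either of two criteria but left by meeting one, so a subject who meets exactly one must enter and already qualifies to leave

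*Protocol*

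**What the plan says.** **Entry.** Section 1.5 states the test at the end-of-study visit as "eosinophil count in peripheral blood is not at least 100 eosinophils/mm³ OR the peripheral blood eosinophil count has not returned to at least 70", where the last figure is a percentage of baseline. The Study Abstract (Subject Evaluation and Follow-up), the footnotes to Tables 4 and 5, and the Long-term Follow-up paragraphs of Sections 3.4.1 and 3.4.2 join the two failures with the same OR. So does Section 3.6, whose second limb is a count that "has not returned to at least 70% of the baseline value at the End of Study/Study Termination".

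**Exit.** Three places say when follow-up stops. Section 1.5: "the subject will return for follow-up every other month until the eosinophil count meets one of the criteria above". The Study Abstract: "the subject will return to the study site every other month until the subject's eosinophil count meets one of the criteria above". Section 3.6: "every other month until the eosinophil count in peripheral blood meets one of the criteria above". The table footnotes and Sections 3.4.1 and 3.4.2 give the entry rule with no exit rule.

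**SAE window.** Section 4.2.2 sets the end of SAE reporting for Cohort 1 as "through Study Day 84 or until eosinophil levels in peripheral blood are at least 100 eosinophils/mm³ OR the peripheral blood eosinophil count has returned", and for Cohort 2 as "through Study Day 140 or until eosinophil levels in peripheral blood are at least 100 eosinophils/mm³ OR the peripheral blood eosinophil count has returned". In both sentences the second limb is the same 70% threshold, with a qualifier at the end: "the peripheral blood eosinophil count has returned to at least 70% of the baseline value, if applicable". The abstract's endpoint section and Section 5.5 carry SAE reporting through the end of long-term follow-up where that applies.

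**The concern.** A follow-up rule works only if the condition for leaving is the negation of the condition for entering. Here the entry rule treats recovery as needing both criteria, while the exit rule and the SAE window treat it as needing one. For a subject with one criterion met, the entry rule calls for return visits every two months with a blood count and an SAE check. The exit rule and Section 4.2.2 say that nothing further is due.

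Long-term follow-up is the only scheduled series of visits after Day 84 or Day 140, and SAEs collected in it count towards the safety summaries. The wording therefore decides who is seen again and when SAE collection stops. Staff working from the schedule tables or the visit lists cannot resolve the conflict, because those places contain no exit rule.

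**Working it through.** The protocol states no figure that could be reproduced here. The check is one of logic, followed by the range of counts affected.

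**Inputs.** A = count at least 100/mm³. B = count at least 70% of baseline. Both thresholds come from Section 1.5.

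- Entry as written: (not A) OR (not B).
- Exit as written: A OR B.
- SAE window closes (Section 4.2.2): A OR B.

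The negation of (not A) OR (not B) is A AND B, which is not the exit rule.

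| A met | B met | Must enter | Meets exit rule and SAE closing condition | Conflict |
|---|---|---|---|---|
| no | no | yes | no | no |
| no | yes | yes | yes | **yes** |
| yes | no | yes | yes | **yes** |
| yes | yes | no | yes | no |

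Two of the four states conflict.

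**Range of counts.** The two thresholds coincide when 0.70 × baseline = 100, that is at baseline = 100 / 0.70 = 142.9/mm³. Above that baseline the conflict runs from 100 to just below 0.70 × baseline (A met, B not). Below it, the conflict runs from 0.70 × baseline to just below 100 (B met, A not). The protocol gives no baseline counts, so these baselines are assumptions:

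| Assumed baseline (/mm³) | 0.70 × baseline | Counts in conflict (/mm³) |
|---|---|---|
| 100 | 70 | 70 to <100 |
| 200 | 140 | 100 to <140 |
| 300 | 210 | 100 to <210 |
| 400 | 280 | 100 to <280 |
| 600 | 420 | 100 to <420 |

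Example: with an assumed baseline of 400 and an end-of-study count of 150, the ratio is 150 / 400 = 37.5%. B fails, so the subject must enter. A holds, so the subject already meets the exit rule and the SAE closing condition.

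**Wordings that remove the conflict.**

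- (i) Enter if neither A nor B is met; leave when at least one is met: 0 of 4 states conflict.
- (ii) Enter if either is failed; leave only when both are met: 0 of 4 states conflict.

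Wording (i) changes the seven statements of the entry rule. Wording (ii) changes the three statements of the exit rule and the two SAE-window sentences in Section 4.2.2. Either way, an exit rule is needed where only entry is given.

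**The case against.** The best answer is that a coherent reading exists. The exit wording and Section 4.2.2 both treat recovery as meeting one criterion, which suggests that entry was meant for subjects meeting neither. On that view the entry OR is a slip in negating a compound condition. This is plausible, but seven places write entry as failing either criterion and none says neither, so the text does not establish it.

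The consequence is also limited. A subject in the overlap whose count stays there would be released at once or at the first return visit, at a likely cost of no more than one extra blood count and SAE check. Subjects failing both criteria enter and stay under either reading. This stands, and it bounds the harm.

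A reader might infer more than the documents support:

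- **That this is the only safety follow-up after end of study.** It is the only scheduled visit series. Section 4.2.2 also requires SAEs to be followed to resolution beyond the reporting period, and suspected related SAEs learned of later to be reported at any time.
- **That many treated subjects will fall in the overlap at the 12-week visit.** Section 1.4 reports eosinopenia lasting up to 12 to 16 weeks after single IV doses of 1.0 and 3.0 mg/kg. It gives no baseline counts, no course of recovery and nothing on this point for three SC doses. A subject still fully depleted would ordinarily fail both criteria and lie outside the overlap.
- **That SAE windows will differ by site, or that the primary endpoints are compromised.** Differing application is possible but not shown, since Section 4.2.2 does state one closing condition. AE summaries stop at Day 84 or Day 140, and the biopsy endpoint does not use this rule.

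**Conclusion.** The contradiction is in the current text and follows from logic alone: two of four states both require entry and satisfy exit. The overlap exists at every baseline except about 143/mm³, and above that value it widens as baseline rises. Its width for a given subject rests on baselines that the protocol does not give, and the number of subjects affected cannot be derived.

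The reach is modest. It concerns which subjects have scheduled blood counts and SAE checks after end of study, and when their SAE window closes. Cohort 1 (13 subjects) has completed the study, so this falls mainly on Cohort 2, planned at 12 with a maximum of 15. Sample size, the AE summaries and the biopsy endpoint are unaffected. It is still more than a clerical matter, because the two readings give different follow-up to the same subject.

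**What to change.** Reconcile the passages. State one definition of eosinophil recovery, and write entry, exit and the SAE reporting window as exact complements of it in the Study Abstract, Section 1.5, the footnotes to Tables 4 and 5, Sections 3.4.1, 3.4.2 and 3.6, and Section 4.2.2. Add the exit rule where only the entry rule now appears. Which definition applies is a clinical decision for the sponsor, and this review takes no position on it. The change is best made before Cohort 2 subjects reach Day 140.

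The cost is wording in one amendment and, depending on the definition chosen, possibly a few more or fewer follow-up blood counts.
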